5.3.1	Participant Inclusion Criteria	23
5.3.2	Participant Exclusion Criteria	23
5.3.3	Temporary Delay Criteria (Visits 1 and 2)	24
5.3.4	Recruitment	25
5.3.5	Enrollment	26
5.3.6	Participant Withdrawal	27
5.4	STUDY SCHEDULE, PROCEDURES, & EVALUATIONS.....	27
5.4.1	Schedule of events and data collection	27
5.4.2	Randomization	32
5.4.3	Deviation from Protocol	33
5.5	DATA COLLECTION.....	33
5.5.1	Participant Demographics and Vaccine History	33
5.5.2	Follow-up Surveillance for Vaccine Reactogenicity and Safety and Self-Reported ARI or Change in Health Status Resulting in Hospitalization	33
5.5.3	Study Product Supply, Storage, and Administration	34
5.5.4	Biospecimens Collection & Handling	35
5.6	VACCINE SAFETY AND REACTOGENICITY.....	36
5.7	MEDICAL RECORD EXTRACTION.....	36

[figure not shown]
5.7.1	Prior Vaccination	36
5.7.2	Prior Lab-Confirmed Illness	37
6	HUMAN SUBJECTS PROTECTIONS	37
6.1	INSTITUTIONAL REVIEW BOARD REVIEW.....	37
6.2	PARTICIPANT CONFIDENTIALITY	38
6.3	RISKS AND BENEFITS TO PARTICIPANTS.....	39
6.4	RETURN OF RESULTS	41
6.5	COMPENSATION.....	42
7	DATA MANAGEMENT, TRANSFER, AND SECURITY	42
7.1	DATA MANAGEMENT AND TRANSFER.....	42
7.2	DATA SECURITY.....	43
8	STATISTICAL ANALYSIS	44
8.1	STUDY POPULATIONS.....	44
8.2	ANALYSIS PLAN OF YEAR 2 COMPONENT D.....	44
	REFERENCES.....	46
	LAB APPENDICES	47
	LAB APPENDIX A: RESPIRATORY SPECIMEN TESTING FOR INFLUENZA.....	48
	LAB APPENDIX B: HUMAN SERA COLLECTION GUIDELINES FOR INFLUENZA SEROLOGY.....	49
	LAB APPENDIX C: PERIPHERAL BLOOD MONONUCLEAR CELLS	50

[figure not shown]
PROTOCOL SUMMARY

Title:	Randomized study of the immunogenicity and duration of antibody response against circulating SARS-CoV-2 variant and influenza viruses following concomitant versus sequential administration of mRNA COVID-19 vaccine and quadrivalent cell culture-based influenza vaccine among children and adults
Phase:	Phase IV
Population:	600 persons aged 18-64 years and 200 children aged 6-11 years for whom a single dose of 2023-24 influenza vaccine and a single dose of mRNA COVID-19 vaccine is indicated as recommended by ACIP
Clinical Sites:	Four study sites: Arizona State University Tempe; University Hospitals of Cleveland; Washington University St. Louis; University of Pittsburgh
Coordinating Site:	Duke University
Study Duration:	12 months total Enrollment: Aug — Oct 2023 Vaccination: Aug — Nov 2023 Blood draws: Aug 2023 — May 2024 Active surveillance for illness: Aug 2023 — May 2024 Laboratory testing: Nov 2023 — Jul 2024
Participant Duration and Number of Participants:	
 • Up to 10 months (Aug 2023 — May 2024) • 800 total participants (600 aged 18-64 years, 200 aged 6-11 years) at 4 sites (only two sites will enroll children aged 6-11 years)
Randomization:	Adults aged 18-64 years, 2:1:1 permuted block randomization 
 i. Concomitant cclIV4 + COVID-19 mRNA (day 0) [n = 300] ii. Sequential cclIV4 (day 0), COVID-19 mRNA (day 28) [n = 150] iii. Sequential COVID-19 mRNA (day 0), cclIV4 (day 28) [n = 150]

	
Children aged 6-11 years, 2:1:1 permuted block randomization
 
 i. Concomitant ccIV4 + Moderna COVID-19 mRNA (day 0) [n = 100] ii. Sequential ccIV4 (day 0), Moderna COVID-19 mRNA (day 28) [n = 50] iii. Sequential Moderna COVID-19 mRNA (day 0), ccIV4 (day 28) [n = 50]

Description of Study Procedures:
	
This study is a randomized immunogenicity study in an enrolled cohort with active surveillance for acute respiratory illness (ARI). During this study, participants will be randomly assigned to receive an approved quadrivalent influenza vaccine (Flucelvax [ccIV4]) and mRNA COVID-19 vaccine (Moderna) either concomitantly (given in contralateral arms) or sequentially (28 days apart).
 
Blood samples from participants will be collected for measurement of biomarkers of immune response at baseline (visit 1; day 0), post-vaccination 1 (visit 2; day 28), post-vaccination 2 (visit 3; day 56), and post-season (visit 4; day 180). Serum and peripheral blood mononuclear cells (PBMC) and plasma (target to collect PBMC and plasma samples at every visit from a subset of approximately 250 participants; 200 adults and 50 children) samples will be isolated from whole blood and tested for biomarkers of vaccine immunogenicity, and duration of antibody responses.

	
Participants will receive electronic surveys via email or text message three days after each vaccination asking about vaccine reactogenicity and weekly asking about change in health status and new ARI symptoms; those reporting illness may be asked to provide a respiratory swab for laboratory testing for influenza and SARS-CoV-2 and up to 2 additional blood draws (acute [< 10 days after symptom onset] and convalescent [28 days after acute visit if lab-confirmed positive for influenza or SARS-CoV-2]).

Specimen Collection:
	
Adults aged 18-64 years, n = 600
 
 i. Sera [n = 600] ii. PBMC [target n = 200] 
Children aged 6-11 years, n = 200
 
 i. Sera [n = 200] ii. PBMC [target n = 50]

Objectives:
	
Primary Objective:
 
 i. Determine baseline and post-vaccination influenza antibody titers by hemagglutination inhibition (HAI) (in a subset) against cclIV4 vaccine antigens following concomitant administration with mRNA vaccine or alone 
Exploratory Objective:
 
 ii. Determine baseline and post-vaccination influenza antibody titers by microneutralization (MN) (in a subset) against cclIV4 vaccine antigens following concomitant administration with mRNA vaccine or alone iii. Determine baseline and post-vaccination SARS-CoV-2 antibody binding titers and ACE2 binding inhibition and viral neutralization, on a subset of specimens, against Moderna mRNA COVID-19 vaccine antigens following concomitant administration with cclIV4 or alone iv. Determine duration and rate of waning of influenza HAI and MN antibody titers against cclIV4 vaccine antigens and circulating influenza viruses v. Determine duration of and rate of waning of SARS-CoV-2 binding antibody and neutralization titers (in a subset of specimens) against Moderna mRNA COVID-19 vaccine antigens and circulating SARS-CoV-2 variants
---------------------------	--

	
 vi. Determine influenza HAI and MN antibody titers against circulating influenza viruses during baseline and post-vaccination vii. Determine SARS-CoV-2 antibody binding titers and viral neutralization titers (in a subset of samples) against circulating SARS-CoV-2 variants during baseline and post-vaccination viii. Compare the frequencies of antigen-specific T and B cells utilizing high-dimensional flowcytometric analysis of innate and adaptive immune cell phenotype characterization using fluorochrome-conjugated antigen tags, and intracellular cytokine staining to 2023-24 cclIV4 and mRNA COVID-19 vaccines administered either concomitantly or sequentially, 28 days apart ix. Compare transcriptome, B cell receptor (BCR) and T cell receptor (TCR) diversity of antigen-specific cells and assess serological antibody repertoire (clonotypes) using 10X genomics platform, and liquid chromatography/mass spectroscopy in a subset of participants x. Investigate the waning of antigen-specific B cells and antibody clonotypes in a subset of participants xi. Describe safety of concomitant versus sequential administration of cclIV4 and mRNA COVID-19 vaccination

Outcome Measures:
	
Primary Outcome Measures:
 
 i. The percent seroconversion and seroprotective titer, the geometric mean titer (GMT), and geometric mean fold rise (GMFR) in titer for each vaccination group across HAI titers for each 2023-24 influenza vaccine antigen 
Exploratory Outcome Measures:
 
 ii. The percent seroconversion and seroprotective titer, the geometric mean titer (GMT), and geometric mean fold rise (GMFR) in titer for each vaccination group across MN titers for each 2023-24 influenza vaccine antigen iii. GMT for SARS-CoV-2 binding antibody titer and viral neutralization titer (for a subset of samples) pre- and post-vaccination with mRNA COVID-19 vaccine iv. GMT and geometric mean fold change in HAI or MN titers at baseline, post-vaccination, mid-season, and post-season against 2023-24 circulating influenza virus and influenza vaccine antigens

	
 v. GMT and geometric mean fold change for SARS-CoV-2 binding antibody and the neutralization titer (for a subset of samples) at baseline, post-vaccination, mid-season, and post-season against 2023-24 circulating SARS-CoV-2 virus and mRNA COVID-19 vaccine antigens vi. Percent seroconversion and seroprotective titer, GMT, GMFR in HAI or MN titers at baseline and post-vaccination against 2023-24 circulating influenza virus antigens vii. GMT and GMFR for SARS-CoV-2 binding antibody and the neutralization titer (for a subset of samples) at baseline and post-vaccination against 2023-24 circulating SARS-CoV-2 virus antigens viii. The frequency of antigen-specific T and B cells to influenza and SARS-CoV-2 at baseline, post-vaccination, mid-season and post-season, high-dimensional flowcytometric analyses of innate and adaptive immune cells, and ELISPOT evaluation for SARS-CoV-2 memory B cells ix. BCR and TCR diversity and clonal dominance (antibody clonotypes) of serological repertoire in a subset of participants x. The frequency of antigen-specific B cells and clonal dominance (antibody clonotypes) to influenza and SARS-CoV-2 at baseline, post-vaccination, mid-season and post-season in a subset of participants xi. Number and percent of participants reporting fever or injection site and systemic reactions during the first 3 days following each vaccination and a change in health requiring hospital admission during the study period

Estimated Time to Complete Enrollment:
	
3 months: Aug — Oct 2023

1 TITLE OF PROJECT

Randomized study of the immunogenicity and duration of antibody response against circulating SARS-CoV-2 variant and influenza viruses following concomitant versus sequential administration of mRNA COVID-19 vaccine and quadrivalent cell culture-based influenza vaccine among children and adults

Short Title: Comparative immunogenicity of concomitant vs sequential mRNA and influenza vaccination

1.1 Study Sponsor

Influenza Division, U.S. Centers for Disease Control and Prevention

2 ABBREVIATIONS

ACE2	Angiotensin Converting Enzyme 2
ARI	Acute Respiratory Illness
BCR	B cell receptor
ccIV4	Flucelvax Quadrivalent
GMT	Geometric Mean Titers
GMFR	Geometric Mean Fold Rise
HAI	Hemagglutination Inhibition
IRB	Internal Review Board
LAR	Legally Authorized Representative
MN	Microneutralization
PBMC	Peripheral Blood Mononuclear Cells
RT-PCR	Reverse-Transcription Polymerase Chain Reaction
SAE	Serious Adverse Event
TCR	T cell receptor

3 BACKGROUND

3.1 *Protocol Summary*

This protocol describes an immunologic study of response to influenza and SARS-CoV-2 vaccination across four of the US Influenza Vaccine Effectiveness (Flu VE) Network study sites. This protocol meets the objectives of component D in the Flu VE Network Cooperative Agreement (IP16-004), including enrollment of eligible persons into a cohort, administration of a licensed or authorized under emergency use authorization (EUA) mRNA COVID-19 vaccine (Moderna COVID-19 Vaccine) and licensed quadrivalent cell culture-based influenza vaccine (Flucelvax; ccIV4), collection and testing of blood specimens, administration of enrollment surveys, protection of personally identifiable information, transfer of a HIPAA-limited dataset to the Network Coordinating Center (NCC) and CDC, and creation of a coded individual-level dataset according to a data management agreement.

3.2 Protocol Background and Rationale

Current guidance concerning administration of U.S.-approved or -authorized COVID-19 vaccines indicates that these vaccines may be given with influenza vaccines.¹

In accordance with general best practices, routine administration of all age-appropriate doses of vaccines concomitantly is recommended for children, adolescents, and adults for whom no specific contraindications exist at the time of the healthcare visit. Providers should be aware of the potential for increased reactogenicity with concomitant administration and should consult updated CDC guidance as more information becomes available.

Extensive experience with non-COVID-19 vaccines has demonstrated that immunogenicity and adverse event profiles are generally similar when vaccines are administered concomitantly as when they are administered alone.

Studies that compared coadministration of COVID-19 vaccines and seasonal influenza vaccines with separate administration of these vaccines found similar levels of immunogenicity and similar or slightly higher reactogenicity;²⁻⁴ no specific safety concerns were identified.

During the 2023-2024 influenza season, CDC plans a randomized influenza vaccine immunogenicity study to compare immune responses to concomitant vs sequential administration of licensed or authorized vaccines for COVID-19 and influenza in select age groups. For future seasons, immunogenicity studies may enroll different age groups each season depending on the vaccines to be compared. To study immune responses to vaccination, each study site will recruit and enroll up to 250 participants who are eligible to receive specific influenza and COVID-19 vaccines and for whom the vaccines are recommended. Study sites will implement common protocols developed in collaboration with CDC. Data will be combined across sites so that all sites will contribute to a total anticipated sample size of 800 participants for comparisons of immune responses by vaccine administration schedule. Investigators will collect, process, store, and ship sera, plasma, and PBMC specimens to a designated CDC laboratory for testing. Some additional specimen testing may be performed by a CDC-approved site.

Investigators will participate in cross-site decisions on specific influenza and COVID-19 vaccines to be administered, populations to be examined, and interpretation of influenza vaccine response findings. Enrolled participants may either reside or work in settings that facilitate active weekly surveillance for ARI and influenza virus and SARS-CoV-2 infection. To improve representation of specific population groups, study sites may use enrollment quotas for participant demographics including race and ethnicity. To identify influenza virus and SARS-CoV-2 infections, participants will respond to weekly automated electronic surveys to report new ARI symptoms and test results, if applicable. Participants may have the opportunity to provide specimens for standard point of care respiratory testing and up to 2 additional blood draws (at acute illness and 28 days after PCR-confirmed influenza or SARS-CoV-2 infection) if they report qualifying ARI symptoms during weekly surveillance. Participants will provide scheduled blood

samples at enrollment (before vaccination) and at several timepoints after vaccination to measure and monitor humoral and cell-mediated immune (CMI) responses to vaccination. Participants will respond to an automated electronic survey 3 days following each vaccination visit to report the occurrence of fever, injection site reactions, systemic reactions, the severity of reactions and their impact on health. The weekly automatic electronic survey will also request participants to report the occurrence of any change in health requiring hospitalization.

3.3 Vaccines Background and Rationale

3.3.1 COVID-19 Vaccines

COVID-19 vaccines available in the United States are effective at protecting people from getting seriously ill, being hospitalized, and dying from SARS-CoV-2. U.S.-licensed or authorized under EUA mRNA COVID-19 vaccine used in this study will contain the recommended composition to be used as a booster dose at the time of enrollment. Currently, CDC recommends one bivalent vaccine dose for everyone aged 6 years and older that have not previously been vaccinated or have only received monovalent doses if it has been at least 2 months since their last dose.⁵

Two COVID-19 vaccine manufacturers, Pfizer and Moderna, have developed updated (bivalent) COVID-19 boosters. The updated (bivalent) boosters are called “bivalent” because they protect against both the original or ancestral virus that causes COVID-19 and the Omicron variant BA.4 and BA.5. Primary series doses and previous boosters are called “monovalent” because they were designed to protect against the original virus that causes COVID-19. They also provide some protection against Omicron, but not as much as the updated (bivalent) boosters. The virus that causes COVID-19 has changed over time. The different versions of the virus that have developed over time are called variants. As variants continue to evolve it remains unclear at this time what the composition of future booster doses of COVID-19 vaccine. The latest Moderna COVID-19 vaccine will be administered in this trial.

3.3.2 Influenza Vaccines

U.S.-licensed 2023-2024 cell culture-based influenza vaccine used in this study will contain components from four influenza viruses antigenically similar to those recommended by FDA for cell culture–based vaccines: an influenza A(H1N1)pdm09 virus; an influenza A(H3N2) virus; an influenza B/Victoria lineage virus; and an influenza B/Yamagata lineage virus. Most commonly, seasonal influenza vaccines are produced using egg-grown viral isolates; however, this approach could lead to individual’s receiving a boost in antibody protection against egg-adapted antigens which may vary from circulating influenza viruses.¹⁻⁴ Previous work in adults has suggested that vaccination with cell culture-based derived vaccines could improve immune response to circulating influenza viruses compared to traditional egg-based vaccines.⁶⁻⁸

A cell culture-based influenza vaccine, Flucelvax Quadrivalent (cclIV4), will be administered in this trial.⁹ cclIV4 may be administered concomitantly or sequentially with other inactivated vaccines. Injectable vaccines that are given concomitantly should be administered at separate anatomic sites.

Standard-dose, nonadjuvanted cell culture-based vaccine, Flucelvax Quadrivalent (cclIV4) contains 15 µg of HA per vaccine virus in a 0.5-mL dose. cclIV4 is approved for persons aged ≥6 months. Egg-based and cell culture-based vaccines differ in the substrate in which reference vaccine viruses supplied to the manufacturer are propagated in quantities sufficient to produce the needed number of doses of vaccine. For Flucelvax Quadrivalent, reference vaccine viruses are propagated in Madin-Darby canine kidney cells instead of eggs.

4 STUDY OBJECTIVES AND OUTCOME MEASURES

OBJECTIVE	OUTCOME
4.1 Primary	
Determine baseline and post-vaccination influenza antibody titers by hemagglutination inhibition (HAI), in a subset of samples, against vaccine antigens following concomitant administration with mRNA vaccine or alone	
 i. Proportion of participants in each vaccination group with a seroprotective HAI (in a subset of samples) titer (≥1:40) pre- and post-cclIV4 immunization for each 2023-24 influenza vaccine antigen ii. Proportion of participants in each vaccination group achieving HAI (in a subset of samples) seroconversion (a titer ≥1:40 following cclIV4 if the baseline titer is <1:10 or a four-fold rise in titer if the baseline titer is >1:10) following cclIV4 vaccination for each 2023-24 influenza vaccine antigen iii. HAI (in a subset of samples) GMT for each 2023-24 influenza vaccine antigen pre- and post-cclIV4 in each vaccination group iv. GMFR in HAI (in a subset of samples) titers for each 2023-24 influenza

	vaccine antigen in each vaccination group

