4.2 Exploratory	
Determine baseline and post-vaccination influenza antibody titers by microneutralization (MN), in a subset of samples, against vaccine antigens following concomitant administration with mRNA vaccine or alone	
 i. Proportion of participants in each vaccination group with a seroprotective MN (in a subset of samples) titer ($\geq 1:40$) pre- and post-cclIV4 immunization for each 2023-24 influenza vaccine antigen ii. Proportion of participants in each vaccination group achieving MN (in a subset of samples) seroconversion (a titer $\geq 1:40$ following cclIV4 if the baseline titer is $< 1:10$ or a four-fold rise in titer if the baseline titer is $> 1:10$) following cclIV4 vaccination for each 2023-24 influenza vaccine antigen iii. HAI (in a subset of samples) MN for each 2023-24 influenza vaccine antigen pre- and post-cclIV4 in each vaccination group i. GMFR in MN (in a subset of samples) titers for each 2023-24 influenza vaccine antigen in each vaccination group
Determine baseline and post-vaccination SARS-CoV-2 antibody binding titers and ACE2 binding inhibition and viral neutralization, on a subset of specimens, against mRNA COVID-19 vaccine antigens following concomitant administration with cclIV4 or alone	
 i. GMT for SARS-CoV-2 binding antibody titer and viral neutralization titer (for a subset of samples) pre- and post-vaccination with mRNA COVID-19 vaccine
Determine duration and rate of waning of influenza HAI and MN antibody titers	
 i. HAI and MN GMT for each 2023-24 influenza vaccine and circulating influenza virus antigens at visit 1, visit

against cclIV4 vaccine antigens and circulating influenza viruses
	
2, visit 3, and visit 4 for each vaccination group
 
ii. Geometric mean fold change in HAI and MN titers for each vaccination group from visit 1 to visit 2, visit 3, and visit 4 for each 2023-24 influenza vaccine and circulating influenza virus antigen

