8.2 Analysis Plan of Year 2 Component D

HAI antibody titers will be compared between groups receiving the mRNA COVID-19 and cclIV4 influenza vaccines concomitantly or sequentially for each of the four influenza vaccine strains contained in the respective vaccines for that season as well as circulating influenza viruses and SARS-CoV-2 variants. Specifically, we will assess the following objectives:

Primary Objective 1a: Compare the proportion of participants in each vaccination group with a seroprotective HAI titer ($\geq 1:40$) pre- and post-cclIV4 immunization for each cclIV4 antigen. These proportions will be compared between vaccination groups using an exact Mantel-Haenszel statistic.

Primary Objective 1b: Compare the proportion of participants in each vaccination group achieving seroconversion following cclIV4 (an HAI titer $\geq 1:40$ following cclIV4 immunization if the baseline titer is $< 1:10$ or a four-fold rise in HAI titer if the baseline titer is $> 1:10$) for each cclIV4 antigen. These proportions will be compared between vaccination groups using an exact Mantel-Haenszel statistic.

Primary Objective 1c: Compare the GMT for each cclIV4 antigen and circulating influenza viruses pre- and post-cclIV4 immunization in each vaccination group. GMT will be compared between vaccination groups using a regression model.

Primary Objective 1d: Compare the GMFR in HAI titer for each vaccination group. GMFR will be compared between vaccination groups using a mixed effects regression model with a random intercept.

Exploratory objectives will be assessed using exact Mantel-Haenszel statistics to compare proportions between vaccination groups, regression models to compare GMT, and mixed effects regression models to compare GMFR. Tables will be provided summarizing counts and proportions for categorical outcomes or summary statistics and confidence intervals for

continuous outcomes. The statistical analysis of each exploratory objective will be fully described in the statistical analysis plan (SAP).

HAI titers will be log transformed prior to analysis and back transformed to estimate GMT and GMFR. The same analysis plan for HAI titers will be repeated for MN titers.

Data analysis will be performed using SAS version 9.4 software (SAS Institute Inc., Cary, NC) or R software (R Core Team, Vienna, Austria).

REFERENCES

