### 3 STUDY ENDPOINTS

#### 3.1 Primary

- i. Proportion of participants in each vaccination group with a seroprotective HAI (in a subset of samples) titer ( $\geq 1:40$ ) pre- and post-cclIV4 immunization for each 2023-24 influenza vaccine antigen
- ii. Proportion of participants in each vaccination group achieving HAI seroconversion (a titer  $\geq 1:40$  following cclIV4 if the baseline titer is  $< 1:10$  or a four-fold rise in titer if the baseline titer is  $> 1:10$ ) following cclIV4 vaccination for each 2023-24 influenza vaccine antigen
- iii. HAI GMT for each 2023-24 influenza vaccine antigen pre- and post-cclIV4 in each vaccination group
- iv. GMFR in HAI titers for each 2023-24 influenza vaccine antigen in each vaccination group

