## 9 ANALYSIS OF STUDY OBJECTIVES

### 9.1 Primary Objective

The primary objective will be analyzed using the immunogenicity population. All endpoints will be assessed with two-sided tests and alpha set to 0.05.

*Endpoint i:*

The proportion of participants with a seroprotective HAI before and 28-42 days after immunization will be compared between group i (concomitant administration) and ii (influenza administered first), using the following null ( $H_0$ ) and alternative ( $H_1$ ) hypotheses:

$H_0$ : Simultaneous group – Sequential group = 0

$$H_0: \pi_1 - \pi_2 = 0$$

$$H_1: \pi_1 - \pi_2 \neq 0$$

where  $\pi$  is the seroprotective rate.

P values and confidence intervals for the geometric mean titer ratio will be estimated using a logistic regression adjusted for site.

*Endpoint ii:*

The proportion of participants achieving seroconversion will be compared between group i (concomitant administration) and ii (influenza administered first), using the following null ( $H_0$ ) and alternative ( $H_1$ ) hypotheses:

$H_0$ : Simultaneous group – Sequential group = 0

$$H_0: \pi_1 - \pi_2 = 0$$

$$H_1: \pi_1 - \pi_2 \neq 0$$

where  $\pi$  is the seroconversion rate.

P values and confidence intervals for the geometric mean titer ratio will be estimated using a logistic regression adjusted for site.

*Endpoint iii:*

GMTs before and 28-42 days after immunization will be compared between group i (concomitant administration) and ii (influenza administered first), using the following null ( $H_0$ ) and alternative ( $H_1$ ) hypotheses:

$$H_0: \mu_1 / \mu_2 = 1$$

$$H_1: \mu_1 / \mu_2 \neq 1$$

where  $\mu$  is the geometric mean titer.

P values and confidence intervals for the geometric mean titer ratio will be estimated using a generalized estimating equation linear regression accounting for site clustering.

*Endpoint iv:*

Geometric mean fold rise will be compared between group i (concomitant administration) and ii (influenza administered first), using the following null ( $H_0$ ) and alternative ( $H_1$ ) hypotheses:

$$H_0: \mu_1 / \mu_2 = 1$$

$$H_1: \mu_1 / \mu_2 \neq 1$$

where  $\mu$  is the geometric mean fold rise.

P values and confidence intervals for the geometric mean titer ratio will be estimated using a linear regression adjusted for site.

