### *Serology*

Microneutralization (MN), SARS-CoV-2 binding antibody and viral neutralization, and circulating virus objectives will all use the same statistical methods as the primary HAI objective. Waning objectives will use parametric models to estimate the rate of antibody decline by time since vaccination. Estimated GMTs and fold change will be presented for each time point with their associated 95% confidence intervals.

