## 10 DERIVED AND TRANSFORMED DATA

Values below the limit of detection will be set to half the limit.

HAI and MN titers will log 2 transformed for calculation of GMT and GMFR.

**Fold Rise or Fold Change** is defined as a numeric variable for participants with non-missing values as:

post vaccination titer/pre vaccination titer

**Geometric Mean Titer (GMT)** is calculated by taking the anti-log of the mean of the log transformed titers

**Geometric Mean Fold Rise/Change (GMFR)** is calculated by taking the anti-log of the mean of the log transformed fold rise.

**Seroconversion** is defined as binary variable for participants with non-missing values as:

= 1, if achieving a HI antibody titer  $\geq 1:40$  following influenza vaccination if the baseline titer is  $< 1:10$  or a four-fold rise in titer if the baseline titer is  $> 1:10$

= 0, otherwise

**Seroprotection** is defined as binary variable for participants with non-missing values as:

= 1, if achieving a HI antibody titer  $\geq 1:40$

= 0, otherwise

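### The seroconversion rule has no branch for a baseline titre of exactly 1:10, so as written those participants count as failures whatever their rise

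*Protocol*

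**What the plan says.** Protocol 4.1, outcome ii, has two routes to HAI seroconversion: a titre of at least 1:40 after ccIIV4 "if the baseline titer is <1:10 or a four-fold rise in titer if the baseline titer is >1:10".

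The same pair of strict inequalities (below 1:10, above 1:10) appears in seven other places:

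- Protocol 4.2, microneutralization (MN) outcome ii and circulating-influenza outcome ii ("or a four-fold rise in titer if the baseline titer is" above 1:10)
- Protocol 8.2, Primary Objective 1b ("or a four-fold rise in HAI titer if the baseline titer is" above 1:10)
- SAP 3.1, endpoint ii ("a four-fold rise in titer if the baseline titer is" above 1:10)
- SAP 3.2, EO1 II and EO5 II
- SAP 10, the derived-variable definition

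SAP 10 makes seroconversion a binary variable for everyone with non-missing values and assigns 0 to anyone who meets neither route. It also says "Values below the limit of detection will be set to half the limit", without giving the limit. SAP 9.1 then specifies the test: "The proportion of participants achieving seroconversion will be compared between group i (concomitant administration) and ii (influenza administered first"), two-sided at 0.05. SAP 9.2 adds that MN, SARS-CoV-2 and "circulating virus objectives will all use the same statistical methods as the primary HAI objective".

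**The concern.** A baseline equal to 1:10 falls between the two branches. SAP 10 does not set such a participant to missing; it codes a failure at every post-vaccination titre. Participants just below and just above 1:10 are coded on their response, and no reason is given for treating 1:10 differently.

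The cut at below 1:10 suggests that 1:10 is itself a value the assay can report. If so, the absolute seroconversion rate is understated for every antigen with responders at that baseline. Randomisation does not correct this, because the error lowers the rate in every arm. The effect on the comparison of groups i and ii depends on whether the arms differ among participants at 1:10.

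**Working it through.** **No plan figure to reproduce.** Neither document gives an expected seroconversion rate, a power calculation, the HAI or MN starting dilution, the dilution series or the limit of detection.

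**Step 1: apply the rule literally.** Code 1 if (baseline < 10 and post ≥ 40) or (baseline > 10 and post ≥ 4 × baseline), otherwise 0. Assume a two-fold grid of 5, 10, 20, …, 2560.

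| Baseline | Post-vaccination titre | As written | With ≥1:10 |
|---|---|---|---|
| 5 (below 1:10) | 40 | 1 | 1 |
| 10 | 40 | 0 | 1 |
| 10 | 640 | 0 | 1 |
| 10 | 2560 (256-fold) | 0 | 1 |
| 20 | 80 | 1 | 1 |

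The two codings differ only at baseline 10 with a post titre of 40 or more. Because 4 × 10 = 40, closing the gap from the other side (≤1:10 in the 1:40 branch) gives the same code in every cell.

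The limit-of-detection rule does not help. If the limit were 1:10 (an assumption), undetectable titres would become 5 and a measured 1:10 would stay at 10.

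**Step 2: shortfall in the rate.** Shortfall = f × s, where f is the share at baseline 1:10 and s is their true conversion rate. With f = 10% and s = 50%, it is 5 points: 15 of 300 adults in group i and 7.5 of 150 in group ii.

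To see plausible sizes I simulated 40 scenarios of 400,000 participants each. All inputs are assumed:

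- Latent baseline GMT 10, 20, 40, 80 or 160; SD 1.5 or 2 on the log2 scale.
- GMFR 1.5, 2.5, 4 or 6; rise falling with baseline (slope −0.4, residual SD 1.3).
- Titres floored to two-fold dilutions from 1:10, with lower values set to 5.

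Between 2% and 25% of participants then sit at 1:10.

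| Latent baseline GMT | Shortfall, GMFR 1.5 to 4 (points) |
|---|---|
| 10 | 3.8–14.6 |
| 20 | 5.7–17.5 |
| 40 | 6.1–13.0 |
| 80 | 3.7–8.1 |
| 160 | 1.3–4.1 |

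- Minimum: 1.3 points (GMT 160, SD 1.5, GMFR 1.5; 25.3% reported against 26.5%).
- Middle example: GMT 20, SD 2, GMFR 4; 35.3% against 48.8%.
- Maximum: 20.8 points (GMT 20, SD 1.5, GMFR 6; 49.1% against 69.8%).

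**Step 3: effect on the group i versus ii test.** Two-proportion normal approximation with 300 and 150 adults (Protocol Summary), two-sided 0.05. Rates are assumed. Where two figures are given, the lower uses unpooled and the higher pooled null variance.

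(a) *Arms differ at 1:10 as they do elsewhere.* True rates are 36% and 50%. With share w at 1:10, both rates are multiplied by (1 − w). At w = 0.20:

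- Rates: 0.36 × 0.8 = 28.8% and 0.50 × 0.8 = 40.0%; the difference falls from 14.0 to 11.2 points.
- SE = √(0.288 × 0.712/300 + 0.40 × 0.60/150) = 0.0478.
- Unpooled power = Φ(0.112/0.0478 − 1.96) = 65%; pooled power = 66%.

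| Share at 1:10 | Power |
|---|---|
| 0 | 81% |
| 5% | 77–78% |
| 10% | 73–74% |
| 20% | 65–66% |
| 25% | 61–62% |

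(b) *Arms do not differ at 1:10.* 20% sit at 1:10 and convert at 70% in both arms; the rest convert at 33% and 45%.

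- Corrected rates: 0.2 × 70 + 0.8 × 33 = 40.4% and 0.2 × 70 + 0.8 × 45 = 50.0%.
- As written: 0.8 × 33 = 26.4% and 0.8 × 45 = 36.0%.
- The difference is 9.6 points either way, and power goes from 49% to 54–56%.

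**The case against.** The strongest reply is that the gap may have little or no practical effect, and that it does not bias the comparison.

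- **Reportability.** If 1:10 is never a reported value, nothing changes. The documents do not settle this. That stands, and it is why the size is conditional.
- **Bias.** Baseline is measured before vaccination in a randomised trial, so the share at 1:10 should be similar across arms. Under the null both arms have the same expected rate, and type I error is not inflated. That stands too. Loss of power is possible but not certain, as case (b) shows. Only one of the four primary endpoints uses the rule.
- **The power illustration.** A 14-point difference has no source in the documents, and Protocol 3.2 describes earlier studies as finding similar immunogenicity. Protocol 4.1 restricts HAI to a subset of samples, so the numbers could be smaller than 300 and 150. SAP 9.1 uses site-adjusted logistic regression, not this simple test. The figures show direction and rough size only.
- **Convention.** A programmer may silently use ≥1:10, much as four-fold is normally read as at least four-fold. The derivation program is not in the documents, so this cannot be excluded. But the program would then depart from the written definition of a primary endpoint, and the text would still need correcting.

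A text-extraction fault is unlikely: the at-least sign before 1:40 survives in the same sentences, and the strict sign before 1:10 recurs in all eight.

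**Conclusion.** The concern holds. As written, primary endpoint ii classes every participant with a baseline of exactly 1:10 as a non-seroconverter, and the MN and circulating-virus versions inherit the error. This is an error in a stated rule, not a missing detail.

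Its numerical effect is unknown from the documents. If 1:10 is reportable and some participants there respond, the absolute rates are understated, by 1.3 to 20.8 points across the assumed scenarios. The arm comparison is diluted if the arms differ at 1:10 as they do elsewhere, and otherwise keeps its difference. Because the rule defines a primary endpoint and a later change could look data-driven, it should be corrected before titres are analysed.

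**What to change.** Replace >1:10 by ≥1:10, and state that the rise must be at least four-fold, in:

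- Protocol 4.1 (outcome ii), 4.2 (MN and circulating-virus outcomes) and 8.2 (Objective 1b)
- SAP 3.1, 3.2 (EO1 and EO5) and 10
- the derivation program

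Writing ≤1:10 in the 1:40 branch would work equally well; what matters is that 1:10 belongs to one branch, stated the same way everywhere. In SAP 10, also give the starting dilution and limit of detection for HAI and MN. Report the number of participants at baseline 1:10 by arm and antigen.

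The cost is two short wording changes in eight places, one condition in the program, and a dated amendment because a primary endpoint definition changes. No new data are needed, and no participant at any other baseline is reclassified.
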